Aim 1A: On the day of surgery, patients will be asked about paresthesia and loss of sensation around the umbilicus. We will document the time when normal sensation returns following the administration of the block. The time elapsed (in minutes) between rectus sheath blockade and the point at which normal sensation returns will be compared between the groups.

Aim 1B: Every 2 hours, we will question the patients regarding their need for pain medication and obtain their Numeric Rating Scale (NRS) pain scores for umbilicus incisional pain. We will document when the patient needs pain medication. The time elapsed (in minutes) from the rectus sheath blockade until the first request for umbilicus pain medication, as well as NRS pain scores will be compared between groups.

Hypothesis:

We hypothesize that rectus sheath injections with the ropivacaine/clonidine combination will be superior in providing long lasting analgesia compared to ropivacaine alone, increasing the duration of sensory block and analgesia, and lowering pain scores at the umbilicus incision.

Aim 2. We will determine if any improvements we observe in pain control satisfaction with the ropivacaine/clonidine combination can be attributed to clonidine's ability to reduce anxiety.

Aim 2A will compare between the two groups patient, parent, and nurse NRS satisfaction scores and correlate them with post-op scores on the state-anxiety component of the State-Trait Anxiety Inventory for Children (STAIC S – Anxiety). Aim 2B will compare postoperative

STAIC S – Anxiety scores between the two groups. Aim 2C will compare within the two groups the difference between the pre and post- op STAIC S Anxiety scores to show if ropivacaine/clonidine is more effective at reducing anxiety.

The methodology will be the following:

Aim 2A: NRS pain control satisfaction scores from patient, parent and nurse will be collected at the completion of the study. State-Trait Anxiety Inventory for Children (STAIC S – Anxiety) questionnaires will be administered to both groups before surgery, and at hour 6 after rectus sheath injections. Post-op anxiety scores in each group will be correlated with satisfaction scores. Aim 2B: The postoperative STAIC S – Anxiety scores will be compared between the 2 groups. Aim 2C: The pre-op STAIC S Anxiety scores will be compared with post- op STAIC S Anxiety within each group.

Hypothesis:

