Inclusion criteria will consist of 1) age 10-17 years, 2) scheduled for elective laparoscopic appendectomy, 3) weight $>/=34\text{kg}$, 4) complete postoperative questionnaires. Exclusion criteria will be 1) patients younger than 10 years and 18 years or older, 2) weight $< 34\text{ kg}$, 3) weight $>/=100\text{ kg}$, 4) patient and family refusal, 5) non-English-speaking patients and families, 6) cognitive impairment, 7) developmental delay, 8) allergies to medications used in the study (hydromorphone, oxycodone, acetaminophen, ketorolac, ropivacaine, and clonidine), 9) need for opioids via a patient controlled analgesia device, 10) patients with a positive pregnancy test, and 11) local infection at planned injection sites

The following patients will be excluded from the study: 1) patients with failed rectus sheath blocks, 2) patients that require opioids via a patient controlled analgesia device, 3) patients with laparoscopic procedure converted to open, 4) patients that will not be able to place the time of return to normal sensation within 1 hour of its occurrence (e.g. sleeping), and 5) patients with no follow-up possible. The patients that will be discharged home before the resolution of paresthesia will be excluded from analysis of the first aim.

Randomization:

The operating room pharmacy will perform the randomization using a computer-generated random number table. The study medications will be labeled as study drug and released in identical syringes with a volume of 11 ml each. Two syringes will be released per patient. Each syringe for Ropivacaine Group (total 2) will contain 10 ml of ropivacaine 0.5% and 1ml of normal saline. Each syringe for the Ropivacaine/ Clonidine Group (total 2) will contain 10 ml of ropivacaine 0.5 %, 1 mcg/kg (0.01 ml/kg) of clonidine (100 mcg =1 ml) and normal saline for a total volume of 11 ml. Patients and all members of the care team, except the pharmacist, will be blinded to group allocation.

Intraoperative Study Protocol:

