In the operating room, standard anesthesia monitors will be connected and general anesthesia will be performed as per the anesthesiologist's standard of care. At the completion of surgery, acetaminophen iv and ketorolac will be administered by the anesthesia provider. Dexmedetomidine will not be administered during anesthesia or after the completion of anesthesia. A member of CHP Acute Interventional Perioperative Pain Service (AIPPS) – attending or fellow will perform all bilateral ultrasound guided rectus sheath blocks as per CHP standard of care using the study drug. The surgeon will not infiltrate the local anesthetic at the laparoscopic instrument sites.

Postoperative Study Protocol:

For the following 24 hours, the analgesic regimen will include ketorolac every 6 hours (if not contraindicated by surgeon), acetaminophen iv every 6 hours, oxycodone by mouth as needed for pain, every 4 hours, and hydromorphone iv as needed for pain, every 2 hour.

In the postoperative period the patients will be asked to complete a few questionnaires created for this study. The nurse taking care of the patient, principal investigator, one of the co-investigators, or the research assistant will do the assessment. Starting in the PACU, the patients will be questioned about the presence of paresthesia around the umbilicus instrument site ("is the area around your belly button numb") and the umbilical pain severity using NRS scale (0 being no pain and 10 the worst imaginable pain). They will also be asked about their need for pain medication for umbilical pain as well as the amount of pain medication they have consumed for pain in that region. The assessment will continue on the floor every 2 hours until complete resolution of paresthesia at the umbilicus or until the patient is discharged home. The state version (S-anxiety) of the State-Trait Anxiety Inventory for Children (STAIC) will be administered to measure patient anxiety before surgery after the consent is done and 6 hours after rectus sheath injections. At the completion of the study,

the patient's, parent's, and nurse's satisfaction with pain control will be investigated using an NRS scale (0 being very unsatisfied and 10 being very satisfied).

E. STATISTICS: ASSESSMENT OF ADEQUACY OF SAMPLE SIZE

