Descriptive statistics will be presented as frequencies (percentages, %) for categorical data or as mean \pm standard deviation (SD) or median and interquartile range for normally or non-normally distributed continuous data, as appropriate. Examination of normal distribution assumption for continuous data will be determined by q-q plots and histograms. Two sample T-Test or Wilcoxon-Mann-Whitney test will be performed to determine differences between groups for normally or non-normally distributed continuous data, respectively. Pearson's chi-square or Fisher's exact test, as appropriate, will be used to compare the frequency distribution of categorical variables between the groups. We will compute Pearson correlation coefficient between NRS pain scores and the anxiety scores. If the assumptions for the parametric test are not met, a nonparametric alternative will be used (i.e. Spearman correlation coefficient).

Sample Size and Power:

The target sample size was calculated with the assumption that the duration of block in the group with ropivacaine only is 720 minutes \pm 288 minutes and in the group with ropivacaine and clonidine the duration is 1080 minutes \pm 432 minutes. The difference would be clinically relevant if the duration of blocks with ropivacaine and clonidine will be at least 50% or more than the duration of blocks with local anesthetic only. Assuming a power of 80%, a level of significance of 0.05, mean and SD as above, only 12 patients would be required in each group. Allowing for a 400% loss arising from patient dropout, unsuccessful block, incomplete follow up because of discharge home on the day of surgery, and inability to determine when paresthesia wears off, we plan to recruit 50 patients in each group, for a total of 100 patients. We estimate that this sample size of 100 patients would provide 80% power to detect a difference as small as 23% in the duration of paresthesia between these 2 groups.

F. SIGNIFICANCE AND APPLICABILITY

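### Exclusion 4 removes children according to when their block ends, so the Aim 1A comparison is selected on its own outcome; hard-to-time endings should be kept as interval-censored

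*Combined protocol and SAP*

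**What the plan says.** - **Outcome (section B, Aim 1A).** "The time elapsed (in minutes) between rectus sheath blockade and the point at which normal sensation returns will be compared between the groups". The paragraph says the time of return will be documented, but not how.
- **Schedule (section D, Postoperative Study Protocol).** From the PACU onward the child is asked whether the area is numb. "The assessment will continue on the floor every 2 hours until complete resolution of paresthesia at the umbilicus", or until discharge. Nothing says whether a sleeping child is woken, or what time is assigned when sensation returns between two checks.
- **Exclusion (section D, Patient eligibility, second list, item 4).** The list removes from the study "patients that will not be able to place the time of return to normal sensation within 1 hour of its occurrence (e.g. sleeping"). Its neighbours (failed block, no follow-up possible) show that it is applied after the study drug has been given, hence after randomisation.
- **Discharge (same paragraph).** "The patients that will be discharged home before the resolution of paresthesia will be excluded from analysis of the first aim".
- **Sample size and tests (section E).** The calculation assumes "the duration of block in the group with ropivacaine only is 720 minutes", with an SD of "288 minutes and in the group with ropivacaine and clonidine the duration is 1080 minutes"; the second SD is 432 minutes. Failure to establish when numbness ended is one of the listed reasons for going from 12 to 50 per group. The tests are a two-sample t-test or Wilcoxon test. No method for censored times is given.
- **Status of the outcome (section G).** Duration of paresthesia is preferred to pain scores and analgesic use as the marker of how long analgesia lasts. Section E sizes the trial on it.

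**The concern.** Whether a child contributes an Aim 1A value depends partly on whether the block ended at an hour when the child could notice. That hour is the time of the block plus its duration, and duration is the outcome. The sample is therefore selected on the outcome after randomisation.

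If clonidine works as the plan expects, blocks in the two arms end about 6 hours apart on average. They then meet the night differently. For a late-morning or midday block, the night removes the longer and typical ropivacaine values and the shorter combination values, so the gain is inflated. For an evening block, it removes the shorter and average ropivacaine values, so the gain shrinks.

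At stake is the estimate for the comparison that sizes the trial, set against a relevance threshold of 50% in section E. Recruiting 50 instead of 12 per group replaces lost numbers but does not undo the selection.

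**Working it through.** **1. The plan's own figures.** Take Δ = 1080 − 720 = 360 min, two-sided α 0.05 and power 80%, with n = 2(1.960 + 0.842)² SD²/Δ².
- With SD 288 in both arms: 2 × 7.85 × (288/360)² = 10.05, so 11 per group, or 12 by the t-test. This reproduces the stated 12.
- Detectable difference with 50 per group: 2.80 × 288 × √(2/50)/720 = 22.4% (22.6% by the t-test). This reproduces the stated 23%.
- Using both stated SDs (root mean square 367) gives 17–18 per group and 29%. Fifty per group still leaves a margin in numbers.

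**2. Inputs for the illustration.** From section E: 12 h (SD 4.8 h) and 18 h (SD 7.2 h), a true ratio of 1.5. Assumed, because the documents are silent: normal (positive values), lognormal or gamma shape; sleep 22:00–06:00; every ending in that window untimed; block hours as shown. For each arm:
- loss = P(block hour + T falls in the sleep window)
- retained mean = mean of T given that it falls outside the window
- apparent gain = ratio of retained means − 1

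**3. Worked case: block at 14:00, normal shape.** The window covers 8–16 h and 32–40 h after the block.
- Ropivacaine loss: Φ((16−12)/4.8) − Φ((8−12)/4.8) = 0.595, about 60%.
- Combination loss: Φ((16−18)/7.2) − Φ((8−18)/7.2) = 0.308, plus 0.025 for 32–40 h, about 33%.
- Retained means are 12.2 h and 20.1 h. 20.1/12.2 = 1.65, an apparent gain of 65%.

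**4. Other block times, range over the three shapes.**

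| Block time | Ropivacaine lost | Combination lost | Apparent gain (true 50%) |
|---|---|---|---|
| 10:00 | 36–46% | 42–50% | 88–103% |
| 14:00 | 60–63% | 33–46% | 65–66% |
| 18:00 | 46–58% | 25–28% | 18–29% |
| Even over 08:00–20:00 | 50–52% | 33–41% | 56–59% |
| Even over 24 h | 33% | 33% | 50% |

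The extremes are 18% (18:00, lognormal: 18.9/16.0 = 1.18) and 104% (11:00, normal).

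**5. Milder case.** If only half of overnight endings are untimed, the daytime mix gives 53–54%, and single block hours from 08:00 to 20:00 give 39–66%.

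**6. The 2-hour grid alone.** Scoring each child at the first clear check adds about 1 h to each arm: (18 + 1)/(12 + 1) = 1.46, a gain of 46%. The grid matters little; the exclusion drives the bias.

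**7. Power and type I error.** Simulated trials with 50 per arm and a Welch test after total overnight loss gave about 96–98% power for 14:00 blocks and for the daytime mix. With all blocks at 18:00, power was about 92% for normal durations and 64–80% for skewed ones. If the two arms have the same distribution, they lose the same fraction at every block hour, so the false-positive rate is not inflated.

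**8. Long blocks.** P(T > 24 h) is 1 − Φ((24−18)/7.2) = 20% in the combination arm (17–20% over the shapes), against about 1–2% for ropivacaine. Study Duration estimates 18–24 hours per patient, so the discharge exclusion also acts unequally.

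**The case against.** The strongest defence is that the three passages are a unit, a contact schedule and a tolerance, and need not conflict. A 2-hourly prompt plus the child's recall to within an hour is workable. Section B plans a documented time of return, the checks have no stated night break, and sleeping is only an example of why a time might not be placed. A reader might infer that blocks ending overnight cannot be scored at all. The text does not say so, and some will be timed. This part of the defence stands.

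The defence can add that section E foresees the loss and allows for it. On power this largely stands: only uniformly late blocks with skewed durations bring it to or below 80%. On bias it does not, because a larger sample selected in the same way has the same bias.

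A reader might also take 18% to 104% as the expected error. The documents do not support that. They give no block hours and no sleep window. The range needs total overnight loss and one block hour for every child, and its two ends come from different distributions. A mix of daytime hours gives a bias of a few points, and an even 24-hour spread gives none.

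**Conclusion.** The point holds as an avoidable, outcome-dependent exclusion after randomisation, joined to an analysis that can use only complete times. Its direction cannot be known in advance, because it depends on block hours that the plan does not give.

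On the stated assumptions, a true 50% gain would read about 56–59% for daytime blocks if every overnight ending is lost, and 53–54% if half are. It could be further off, in either direction, if blocks cluster at one time of day. The harm is to the estimate, and to power only in the late-day, skewed case. It does not create false positives under equal distributions. For a pilot, this is a change that should be made because it is cheap; it does not invalidate the design.

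**What to change.** - Delete exclusion 4 for Aim 1A.
- For each child record the last check with altered sensation and the first check with normal sensation, or the child's reported time where it can be placed. If no check is made during sleep, the bracket is wider and the child stays in.
- Analyse Aim 1A as interval-censored, for example with an interval-censored log-rank test or an accelerated-failure-time model.
- Treat children who are discharged or end follow-up while still numb as right-censored at their last check, in place of the present exclusion. This assumes that discharge is unrelated to the remaining block time; the plan should say so.
- Amend the Aim 1A method, the Patient eligibility list and section E to match.

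In simulation with overnight checks skipped, a lognormal accelerated-failure-time model returned gains of 50–54% across the block-time patterns tried. That test used lognormal and gamma durations only and did not include discharge.

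The cost is protocol and analysis wording plus standard software, with no added visits or night wakings. The result becomes a model-based time ratio or a rank-type test instead of a simple difference in means, and wide overnight brackets lose a little precision.

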Minimal sedation can be desired for some pediatric patients that underwent surgeries. Clonidine produces effective sedation for patients on mechanical ventilation that can be uncomfortable because anxiety, pain and endotracheal intubation. (21) Clonidine at 2 mcg/kg prevents sevoflurane-induced agitation (22), (23) and can be used as premedication in children. (24), (25) Oral clonidine can relieve postoperative anxiety, and subsequently improve pain control. (26) No studies have investigated its role as an anxiolytic when added to local anesthetic for a nerve block.

Preliminary studies:

The Children's Hospital of Pittsburgh of University of Pittsburgh Medical Center (CHP of UPMC) has a dedicated service that performs peripheral nerve blocks on a regular basis. Over the last academic year, 190 patients (10-17 years old, 126 patients) that underwent laparoscopic appendectomy had peripheral nerve blocks (rectus sheath and transversus abdominis plane). Our experience suggests that children localized the majority of their pain to the umbilicus instrument site. (6) To treat this pain is crucial, as this pain interferes with eating, bedside activities and ambulation, and can delay discharge.

Our preliminary study (retrospective chart of 50 patients that underwent laparoscopic appendectomy) demonstrates that rectus sheath blocks, which target pain at the umbilicus instrument, are as effective as a combination of transversus abdominis plane and rectus sheath blocks, which target pain at all instrument sites. This is an important finding, as it means that instead of dividing the amount of local anesthetic delivered between four sites,

more anesthetic can be delivered bilaterally to a single location. This can result in analgesia that lasts around 12 hours, which is relatively short for our purposes but still an improvement.

[name] prospective study demonstrates that postoperative pain scores after laparoscopic appendectomies correlate very well with postoperative anxiety (Pearson coefficient =0.539;133 subjects, 11-17 years old). Patients that received regional anesthesia for laparoscopic surgeries reported less anxiety after surgery (Spearman coefficient = -0.143, $p = 0.042$; pending publication; 202 subjects, 11-17 years old). The use of single injection nerve blocks predicts less postoperative pain ($p=0.04$), better mood ($p=0.009$), less catastrophizing thoughts about pain ($p=0.007$).

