Based on our experience and preliminary studies, our goal is to treat the patient comprehensively, rather than just the pain itself; whenever possible, we should seek to decrease postoperative anxiety and improve satisfaction with pain control. Recently, we added clonidine to ropivacaine for rectus sheath blockade and noticed longer lasting paresthesia and analgesia (18-22 hours). Because we did not investigate the anxiolytic properties of clonidine, we do not know if the small increase in analgesia we observed is clinically relevant. The potential benefits for patients, families, and medical providers need to be investigated.

Laparoscopic appendectomy is associated with significant pain and anxiety in pediatric populations. The goal of our study is thus to investigate whether the combination of ropivacaine and clonidine is effective in prolonging analgesia beyond the duration observed with ropivacaine alone for pediatric patients undergoing these procedures. Additionally, we will explore the underlying mechanism that may make this combination better equipped for postoperative pain control, so that we can devise more optimal pain control regimens. Our hypothesis is that ropivacaine/clonidine is a significantly better therapeutic regimen for our patients. The primary aim is to determine if the ropivacaine/clonidine combination is superior in providing long-lasting analgesia. The secondary aim is to determine if the ropivacaine/clonidine combination significantly improves satisfaction with pain control due to the psychological benefits of clonidine.

D. RESEARCH DESIGNS AND METHODS

Overview

This is a double blinded prospective study. Following University of Pittsburgh IRB approval, 100 pediatric patients will be recruited. Following parental written consent and patient assent, these patients will be included in the study.

Patient eligibility

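### Aim 1B observation is scheduled to stop at about each patient's own Aim 1A outcome, so time to first request and NRS pain have no common window and no censoring rule

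*Combined protocol and SAP*

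**What the plan says.** Section B defines two outcomes under the first aim. Aim 1A is the time from block to return of normal sensation. Aim 1B compares the time "from the rectus sheath blockade until the first request for umbilicus pain medication, as well as NRS pain scores will be compared between groups". For Aim 1B the section also says "We will document when the patient needs pain medication", with questions every 2 hours and no end time.

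Section D (Postoperative Study Protocol) puts numbness, umbilical NRS, need for medication and amount consumed into one assessment, to "continue on the floor every 2 hours until complete resolution of paresthesia at the umbilicus or until the patient is discharged home". Study Duration agrees: the study period ends when block resolution has been assessed, estimated at 18-24 hours.

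Section D (Patient eligibility) adds: "The patients that will be discharged home before the resolution of paresthesia will be excluded from analysis of the first aim". Its fourth ground for removal also takes out patients who cannot time the return of sensation to within 1 hour.

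Section E, for continuous data: "Two sample T-Test or Wilcoxon-Mann-Whitney test will be performed to determine differences between groups". It contains no time-to-event method or censoring rule, and does not say what value a patient without a recorded request receives.

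**The concern.** Follow-up for one outcome is ended by another outcome that the treatment is expected to change. If clonidine prolongs numbness as hypothesised, clonidine patients are asked about pain and medication for longer than ropivacaine patients. The discharge exclusion then removes more of the longest blocks from the clonidine arm. These two effects can pull in opposite directions.

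The timing may matter. Section C says of rectus sheath blocks "This can result in analgesia that lasts around 12 hours", and reports 18-22 hours of paresthesia and analgesia after clonidine was added. Section E assumes block durations of 720 and 1080 min (12 and 18 h). First requests may therefore fall close to the moment the record stops. Duration of analgesia sits under the primary aim, and answers or scores not taken after resolution cannot be recovered later.

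**Working it through.** **Inputs from the documents.** Block duration 720 ± 288 min (ropivacaine) and 1080 ± 432 min (clonidine), 50 recruited per group, 12 required per group (section E); 2-hourly visits and the stop rule (section D).

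**The plan's own figure.** With SD 288 in both arms, n = 2(1.96 + 0.84)² × 288²/360² ≈ 10.0, so 11 per group by the normal formula and 12 by the t-based version. The stated 12 reproduces. It concerns block duration; Aim 1B has no sample size calculation.

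**Window before exclusions.** Mean 720 versus 1080 min, a gap of 360 min.

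**Window after the discharge exclusion.** Let everyone be discharged at D (assumed 24 h or 18 h) and z = (D − mean)/SD. The share excluded is 1 − Φ(z); the mean duration among those kept is mean − SD × φ(z)/Φ(z).

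- D = 1440 min: z = 2.50 and 0.83. Excluded 0.6% versus 20%. Mean kept: about 715 versus 927 min.
- D = 1080 min: z = 1.25 and 0. Excluded 11% versus 50%. Mean kept: about 661 versus 735 min.

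**Assumptions for the simulation (not in the documents).** Normal request times with CV 0.4, and correlation 0 to 0.5 with numbness. A request counts if it comes by the 2-hourly visit that detects resolution, or by discharge if earlier. The discharge exclusion is applied, and the t-test uses recorded requests.

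**True delay, mean request 720 versus 1080 min, 50 per arm.** Hand check for ropivacaine, ignoring discharge: request and numbness have the same mean, and the detecting visit adds about 60 min on average. The SD of their difference is 288√2 = 407 at correlation 0 and 288 at 0.5. The recorded share is therefore Φ(60/407) = 0.56 or Φ(60/288) = 0.58. Simulated over both discharge times:

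- Recorded request: 51-58% of ropivacaine and 29-49% of clonidine patients analysed.
- Power: 41-59% (D = 24 h) or 8-13% (D = 18 h).
- With all randomised patients followed to D and a log-rank test: over 99%.

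**True delay, early requests (240 versus 360 min), 50 per arm.** Power is 96-99% at D = 24 h. At D = 18 h it is 62-90%, without counting the detecting visit.

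**No true delay, 50 per arm, mean request 240 to 1080 min.** Rejection runs from about 5% to 23% against a nominal 5%. Not counting the detecting visit, the pattern is:

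- D = 24 h, correlation 0: towards clonidine, up to 23%.
- D = 24 h, correlation 0.5: against clonidine for early requests (13% at 240 min), towards it for late ones (22% at 1080 min).
- D = 18 h, correlation 0: 5-8%.
- D = 18 h, correlation 0.5: against clonidine for early requests (23% at 240 min), about 6% from 720 min on.

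**At 12 per arm** (detecting visit not counted), rejection with no true delay is 4-9%, so inflation is small. Power for 720 versus 1080 min at D = 24 h is 12-16%, against 73% with full follow-up.

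**Changing only the test.** A log-rank test censored at resolution, with the discharge exclusion kept, rejects a true null in 5-7% of trials at correlation 0 but 16-31% at 0.5. The window and the exclusion must change as well.

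**The case against.** The strongest reply is that section B says medication need will be documented and sets no end, while as-needed analgesics belong to a 24-hour regimen, so later requests might be found in the chart. This stands in part. A reader might infer that every later request is certainly lost, and the documents do not establish that. What they show is that section B and section D are unreconciled and that no section plans collection after resolution. The 24 hours describes the analgesic regimen, not outcome assessment. Section G itself warns that analgesics may be taken for other pain, so a charted dose need not identify an umbilical request.

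Second, section G prefers paresthesia to pain and analgesic measures, the sample size rests on block duration, and the study calls itself a pilot. All true, and it limits the weight of the point. But section G's reason is misclassified pain rather than truncated follow-up, and Aim 1B is still compared between groups under the primary aim.

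Third, the 18 h case discharges everyone at the clonidine arm's assumed mean, whereas section F describes stays of at least one day. That case is an illustration. Section E does, however, allow for "incomplete follow up because of discharge home on the day of surgery", so early discharge is part of the plan's own expectation.

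**Conclusion.** The point holds as a defect in the Aim 1B schedule and analysis, and should be fixed. On the stated rules the observation window depends on the patient's own numbness, is expected to differ between arms, and comes with no censoring rule. The numerical effect is conditional on the assumptions above and is not a forecast.

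Three stronger readings are not supported:

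- **That the bias favours clonidine.** It can go either way. At 18 h, correlation 0.5 and mean request 720 min, the shift is about 12-15 min against clonidine (detecting visit not counted).
- **That a real delay would mostly be missed, or that Aim 1B is uninformative.** With near-resolution requests and 24 h stays, about 150-190 of 360 min is still recovered (detecting visit not counted). With early requests and 24 h stays, power is hardly reduced.
- **That the trial's other results are compromised.** This rule does not affect Aim 1A or the 6-hour STAIC. False-positive inflation is also small if only about 12 per arm are analysed.

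**What to change.** - **Section D, Postoperative Study Protocol:** continue the 2-hourly umbilical NRS and medication-request record in every patient to a common horizon (24 h after the block, or discharge if earlier), regardless of numbness. Reconcile section B (Aim 1B) and Study Duration with it.
- **Section D, Patient eligibility:** for Aim 1B, apply neither the exclusion for discharge before resolution nor the exclusion for an untimed return of sensation. Both are related to numbness.
- **Section E:** analyse time to first umbilical request by Kaplan-Meier and log-rank, censored at the horizon or discharge and not at resolution. Compare NRS over the same window. Acknowledge that discharge may be informative, since section F links pain to parents' reluctance to go home.

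In simulation this gave 4-6% false positives at 50 per arm (5-8% at 12). That check used all randomised patients and one fixed discharge time, so it does not cover informative discharge.

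**Cost.** Extra entries per patient = E[(D − resolution time)⁺]/120. At 24 h this is about 6.0 per ropivacaine and 3.4 per clonidine patient, at most 50 × 6.0 + 50 × 3.4 = 470 in all, some overnight. At 18 h it is about 3.1 and 1.4. Study Duration already estimates 18-24 hours per patient. Some early censoring from same-day discharge will remain.
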